## 2. Secondary and Exploratory Efficacy Analyses

Efficacy of secondary and other exploratory outcome measures will be assessed at baseline, midpoint (visit 9), and primary endpoint (visit 16) to examine change in scores over time in the total sample, and separately, by PTSD+ participants and CSO participants.

For each model, a one-way repeated-measures ANOVA with post-hoc contrast comparisons will be conducted to test the effects of the treatment on: PTSD CAPS-5; Significant Others' Responses to Trauma Scale (SORTS); Posttraumatic Stress Disorder Checklist for the DSM-5 (PCL-5); Beck Depression Inventory-II (BDI-II); Emotion Regulation Questionnaire (ERQ); Pittsburgh Sleep Quality Index (PSQI); Posttraumatic Growth Inventory (PTGI); Toronto Alexithymia Scale-20 (TAS-20); Inventory of Psychosocial Functioning (IPF); Revised Conflict Tactics Scale (CTS-2); Trauma and Attachment Beliefs Scale (TABS); and Multiscale Dissociation Inventory (MDI). Relationship distress outcome measures include: Interpersonal Reactivity Index (IRI); Quality of Relationships Inventory (QRI); Miller Social Intimacy Scale (MSIS); Interpersonal Closeness Measure (IPC); and Couples Satisfaction Index (CSI).

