The secondary measure of PTSD symptoms will be the PCL (reported for last month, since last visit, and since last week per Table 4), a self-report measure designed to follow DSM-5 criteria for assessing PTSD. The PTSD Checklist (PCL-5) [137] is a 20-item selfreport questionnaire in which respondents indicate the presence and severity of PTSD symptoms, derived from the DSM-5 symptoms of PTSD [36]. Participants indicate how much distress they have experienced due to symptoms such as "Repeated, disturbing memories, thoughts, or images of a stressful experience from the past," "Trouble remembering important parts of a stressful experience from the past," and "Feeling irritable or having angry outbursts" on a five-point Likert-type scale (1 = not at all, 5 = extremely). The total PCL-5 score (a sum of all 20 items) provides an index of overall PTSD symptom severity. Reports on reliability and validation of the PCL-5 are underway; preliminary comparison with the PCL for DSM IV suggests that the cut-off for PCL-5 is 11 to 14 points lower than for the PCL [137]. Participants will complete the PCL-5 questionnaire, as specified in Table 3: Time and Events. The PTSD+ participant will complete it based on their own symptoms and the CSO participant will complete it based on the PTSD+ participant.

The BDI-II is a 1996 revision of the BDI, a 21-item self-report measure [138, 139] that will serve as a measure of depression according to DSM-IV criteria [140]. The BDI-II has been validated, has high internal consistency and good test/re-test reliability, and is not overly sensitive to daily variations in mood. It takes five to ten minutes to complete [140]. Score cutoffs indicate: 0-13 minimal depression, 14-19 mild depression, 20-28 moderate depression, and 29-63 severe depression. Initial and subsequent studies report that the BDI-II total score has a reliability coefficient of 0.90 to 0.91 and that it is related to other measures of depression symptoms [140, 141]. Higher scores indicate more severe depressive symptoms. Both the participants will complete the BDI-II according to Table 3: Time and Events.

The ERQ is a brief measure of self-reported emotion-regulation. It consists of ten items that is intended to assess means of coping with emotions via changing them, as through reappraisal, or suppressing them [142]. Respondents rate indicate the extent of their

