A blinded IR who will not be present during any of the therapy sessions will administer:

• Structured Clinical Interview for DSM-5 Diagnoses (Research Version) (SCID-RV) to assess eligibility based on Axis I diagnoses, which includes a self-report questionnaire to focus on modules to use based on symptoms for both the PTSD+participant and CSO participant

Page 43 of 89

- SCID-II Axis 2 questionnaire to determine if specific modules of the SCID-II Interview will be conducted to confirm diagnoses of personality disorders
- Last-month CAPS for the PTSD+ participant to assess PTSD symptoms and eligibility, which may be recorded to video in as many instances as necessary to establish inter-rater reliability

The following self-report measures will be completed:

- PTGI (in reference to time since the trauma) for the PTSD+ participant and modified for the CSO participant to rate the PTSD+ participant
- PCL-5 (last month) to assess PTSD symptoms for the PTSD+ participant and modified for the CSO participant to rate the PTSD+ participant.
- TABS to assess trauma related beliefs for the PTSD+ participant and modified for the CSO participant to rate the PTSD+ participant
- MDI to assess dissociative symptomology for the PTSD+ participant and CSO participant
- SORTS to assess partner accommodation for the CSO participant
- BDI-II to assess depression symptoms for both the PTSD+ participant and CSO participant
- PSQI to assess sleep quality for both the PTSD+ participant and CSO participant. PSQI-PTSD Addendum will be assessed for the PTSD+ participant only
- ERQ to assess emotional regulation for both the PTSD+ participant and CSO participant
- TAS-20 to assess emotion recognition, alexithymia for both the PTSD+ participant and CSO participant
- QRI to assess relationship satisfaction for both the PTSD+ participant and CSO participant
- CTS to assess conflict, tactics and aggression for both the PTSD+ participant and CSO participant
- IPF to assess psychosocial functioning for both the PTSD+ participant and CSO participant
- MSIS to assess social intimacy for both the PTSD+ participant and CSO participant
- IRI to assess compassion, empathy and social functioning for both the PTSD+ participant and CSO participant
- IPC for both the PTSD+ participant and CSO participant
- CSI for both the PTSD+ participant and CSO participant, if in a romantic relationship

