5.2.8 Primary Assessment (Visit 16 – Telemedicine Visit)

(30 days post Visit 15; window of -2/+7 days)

The PTSD+ participant and CSO participant will repeat all outcome measures with the IR and meet with the therapists again 30 days after Visit 15. This visit may consist of two meetings that may be completed on separate days, one with the IR and the other with the therapists. Session may be recorded to audio/video.

- a. The therapists will assess suicidal ideation and behavior with the C-SSRS
- b. General Wellbeing will be assessed
- c. Last-month CAPS for the PTSD+ participant only will be performed to assess PTSD symptoms, which may be recorded to video in as many instances as necessary to establish inter-rater reliability
- d. Collect AEs and medications, as described in Sections 8.0 and 9.0

The following self-report measures will be completed at the outcome assessment:

- PTGI (in reference to time since the trauma) for the PTSD+ participant and modified for the CSO participant to rate the PTSD+ participant
- PCL (last month) to assess PTSD symptoms for the PTSD+ participant and modified for the CSO participant to rate the PTSD+ participant
- TABS to assess trauma related beliefs for the PTSD+ participant and modified for the CSO participant to rate the PTSD+ participant
- MDI to assess dissociative symptomology for the PTSD+ participant and CSO participant
- SORTS to assess partner accommodation for the PTSD+ participant and CSO participant
- BDI-II to assess depression symptoms for both the PTSD+ participant and CSO participant
- PSQI to assess sleep quality for both the PTSD+ participant and CSO participant PSQI PTSD addendum will be completed by PTSD+ participant only
- ERQ to assess emotional regulation for both the PTSD+ participant and CSO participant
- TAS-20 to assess emotion recognition, alexithymia for both the PTSD+ participant and CSO participant
- QRI to assess relationship satisfaction for both the PTSD+ participant and CSO participant
- CTS to assess conflict, tactics and aggression for both the PTSD+ participant and CSO participant
- IPF to assess psychosocial functioning for both the PTSD+ participant and CSO participant

- MSIS to assess social intimacy for both the PTSD+ participant and CSO participant
- IRI to assess compassion, empathy and social functioning for both the PTSD+ participant and CSO participant
- IPC for both the PTSD+ participant and CSO participant

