#### CSO Participants Only

• Assess changes in partner accommodation from baseline with the Significant Others' Responses to Trauma Scale (SORTS) at the Midpoint, Primary Endpoint, and Long-term Follow-up at 3 months and 6 months for the CSO participant.

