## **Subject Disposition and Dosing Summary**

All subjects enrolled in the study (i.e., who sign informed consent and complete inclusion/exclusion criteria) will be included in the summary of subject disposition and accountability. No inferential statistical tests will be performed. The tabulation of number of subjects will be displayed for all subjects in the Safety population, in the mITT population, and

in the PP population. The number and percent of subjects who completed or discontinued the study will be reported along with reasons for early termination. Percents will be defined as the number of participants who completed, or number discontinued, over the total number of subjects in the total study sample, and separately, for PTSD+ participants and CSO participants. The timepoint of doses and total MDMA (mg) administered will be summarized for the Safety, mITT and PP populations for the total sample and by PTSD+ participants and CSO participants.

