# 3. Secondary Efficacy Analyses at Secondary Endpoints (Long-Term Follow-up)

Efficacy of outcome measures for long-term follow-up will be assessed at baseline, midpoint (visit 9), primary endpoint (visit 16), 3-month follow-up (visit 17), and 6-month follow-up (Visit 18) to examine changes over time in the total sample, and separately, by PTSD+ participants and CSO participants.

For each model, a one-way repeated-measures ANCOVA with baseline scores as covariates and post-hoc contrast comparisons will be conducted to test the effects of the treatment on: PTSD CAPS-5; Significant Others' Responses to Trauma Scale (SORTS); Posttraumatic Stress Disorder Checklist for the DSM-5 (PCL-5); Beck Depression Inventory-II (BDI-II); Emotion Regulation Questionnaire (ERQ); Pittsburgh Sleep Quality Index (PSQI); Posttraumatic Growth Inventory (PTGI); Toronto Alexithymia Scale-20 (TAS-20); Inventory of Psychosocial Functioning (IPF); Revised Conflict Tactics Scale (CTS-2); Trauma and Attachment Beliefs Scale (TABS); and Multiscale Dissociation Inventory (MDI). Relationship distress outcome measures include: Interpersonal Reactivity Index (IRI); Quality of Relationships Inventory (QRI); Miller Social Intimacy Scale (MSIS); Interpersonal Closeness Measure (IPC); and Couples Satisfaction Index (CSI).

If data is missing from participant dropouts a mixed effect model repeat measures (MMRM) will be used instead of an ANCOVA.

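### The SAP's total-sample secondary models treat 10 dyads as 20 independent subjects, and for PCL-5, PTGI and TABS they count each patient twice

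*SAP*

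**What the plan says.** SAP Efficacy Analyses 2 assesses secondary and exploratory measures at baseline, midpoint and primary endpoint "to examine change in scores over time in the total sample, and separately, by PTSD+ participants and CSO participants". Each model is a one-way repeated-measures ANOVA. Efficacy Analyses 3 extends this to five visits "to examine changes over time in the total sample, and separately, by PTSD+ participants and CSO participants", using a one-way repeated-measures ANCOVA with baseline as covariate. It adds: "If data is missing from participant dropouts a mixed effect model repeat measures (MMRM) will be used instead of an ANCOVA". No covariance structure is given for that fallback.

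The SAP's Subject Disposition and Dosing Summary shows what the total sample is. Its percentages are taken over "the total number of subjects in the total study sample, and separately, for PTSD+ participants and CSO participants", so the total is both roles together.

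Several instruments do not describe the person completing them. For PCL-5, Protocol 5.1.1 says "the CSO participant will complete it based on the PTSD+ participant". Protocol 5.2.8 lists "PTGI (in reference to time since the trauma) for the PTSD+ participant and modified for the CSO participant to rate the PTSD+ participant", and Protocol 5.2.1 lists "TABS to assess trauma related beliefs for the PTSD+ participant and modified for the CSO participant to rate the PTSD+ participant". SAP 3.2 confirms for PCL-5 and PTGI that the CSO's answers concern the PTSD+ participant.

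Protocol 12.0 mentions nesting of repeated measures within participants but not within dyads. It also has relationship satisfaction analysed separately by PTSD status.

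**The concern.** In a one-way repeated-measures model, time is the only factor and the individual is the only repeated unit. Applied to both roles together, it takes the two members of a dyad as unrelated. They attend the same sessions with the same therapists, and each is reporting partly on the same relationship. Two separate problems follow.

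The first is one of meaning and needs no assumption about correlation. On PCL-5, PTGI and TABS the pooled mean combines self-report and partner report on the same 10 patients while the analysis counts 20 subjects. It describes neither the patients' own view nor the CSOs' condition.

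The second is one of inference and depends on correlation. If partners' changes are positively correlated, the pooled standard error is too small and so are the p-values. SAP 6.0 calls any p-value at or below 0.05 statistically significant, and SAP 2.0 says the results will inform a larger study. A pooled average can also dilute a change confined to one role.

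**Working it through.** **The plan's own figure.** Protocol 12.1 gives 62% power for n = 10, effect size 0.8, two-sided 0.05. For a paired t-test, df = 9 and the noncentrality is 0.8 × √10 = 2.53; exact noncentral-t power is 0.616. The figure reproduces. It concerns the primary test only; Protocol 12.1 gives no power for secondary measures.

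**Inputs.** From the documents: 10 dyads, two members each, two-sided 0.05, three visits (Efficacy Analyses 2) or five (Efficacy Analyses 3). Assumed, because the documents are silent: the within-dyad correlation ρ of visit-to-visit deviations, and the ratio of CSO to PTSD+ standard deviations.

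**Standard error.** Let σ² be the variance of an individual's change, equal in both roles. The mean of 20 changes from 10 pairs has variance σ²(1 + ρ)/20. The pooled sample variance has expectation σ²(1 − ρ/19). Hence

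true SE / reported SE ≈ √[(1 + ρ)/(1 − ρ/19)].

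At ρ = 0.3 this is √(1.300/0.984) = 1.15; at 0.5, √(1.500/0.974) = 1.24; at 0.7, √(1.700/0.963) = 1.33. The effective number of subjects, 20/(1 + ρ), is 15.4, 13.3 and 11.8.

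**Type I error.** Null trials were simulated with visit deviations correlated ρ within dyad, equal role variances and sphericity satisfied (100,000 to 200,000 trials per row). Rejection rates at nominal 0.05:

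| ρ (assumed) | 2 visits (baseline to endpoint) | 3 visits | 5 visits, no covariate | Dyad means, n = 10 |
|---|---|---|---|---|
| 0 | 0.050 | 0.050 | 0.051 | 0.050 |
| 0.2 | 0.073 | 0.082 | 0.096 | 0.050 |
| 0.3 | 0.086 | 0.100 | 0.121 | 0.049–0.050 |
| 0.5 | 0.111 | 0.141 | 0.180 | 0.049–0.051 |
| 0.7 | 0.140 | 0.179 | 0.243 | 0.050–0.051 |

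A separate run of 20,000 trials per scenario (Monte Carlo SE about 0.002) covered other cases. At ρ = −0.3 the pooled test is conservative: 0.021 for the contrast and 0.014 for three visits. If CSO changes have half the PTSD+ standard deviation, the three-visit rates at ρ = 0.3, 0.5 and 0.7 are 0.088, 0.123 and 0.150; at one third, 0.079, 0.102 and 0.127.

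**Dilution.** If PTSD+ members change by 0.8 SD and CSO members not at all, the pooled mean change is 0.4 SD. Simulated power of the pooled baseline-to-endpoint test is 0.336, 0.363 and 0.370 at ρ = 0, 0.3 and 0.5. The PTSD+ model alone gives 0.620, 0.624 and 0.615. The 0.8 is borrowed from the CAPS-5 planning value purely for illustration.

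**Which scales.** CAPS-5 is given to PTSD+ participants only. The SAP collects SORTS from one role: "SORTS) at the Midpoint, Primary Endpoint, and Long-term Follow-up at 3 months and 6 months for the CSO participant". Neither can be pooled under the SAP. CSI is completed by romantic couples only, so its pooled count may be below 20. The remaining two-role scales face the inference problem; PCL-5, PTGI and TABS also face the double count.

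**The case against.** The strongest reply is that little rests on these tests. The trial is an open-label pilot not meant to support registration, the affected measures are secondary or exploratory, and the sentence that pools the roles also plans the separate models. A reader who uses those is not misled, and a change confined to one role would be seen there. That stands, and it limits the severity.

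Second, inflation depends entirely on an unknown ρ. At zero there is none, even for PCL-5, PTGI and TABS; what holds there at any ρ is the problem of interpretation. An average over two informants is not meaningless in principle, and counting twice here means two raters per patient, not duplicated records. That also stands, but the SAP neither defines such an average as an estimand nor analyses it with 10 patients as the unit.

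Third, the instrument descriptions are uneven. Protocol Table 4 and 5.1.1 say only that the CSO's TABS is modified; the visit descriptions say it rates the partner. Protocol 5.1.1 and 5.2.8 have both members complete SORTS, contrary to the SAP. PCL-5 and PTGI are the clear cases, and SORTS would join them if both members complete it.

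Fourth, the five-visit column is not exactly a planned model, because Efficacy Analyses 3 uses baseline as a covariate. An F test on four visits, still without the covariate, gives about 11%, 16% and 21% at ρ = 0.3, 0.5 and 0.7. The three-visit column matches Efficacy Analyses 2. Finally, the MMRM's silence on dyads is under-specification, not a stated independence assumption; it still needs filling.

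**Conclusion.** The concern holds. As written, the total-sample models ignore pairing and role, and on PCL-5 and PTGI (and TABS, on the visit descriptions) they combine two reports on each of the same 10 patients. On the two-role scales, the three-visit test at nominal 5% has a true level of about 10%, 14% and 18% at ρ = 0.3, 0.5 and 0.7, somewhat less if CSO changes are less variable, 5% at ρ = 0, and below 5% if ρ is negative. These sizes rest on assumed correlations, equal role variances and sphericity. Positive correlation is plausible because treatment is shared, but the documents do not quantify it. The primary paired t-test, CAPS-5 and the role-specific models are not affected. This should be corrected before analysis, but it does not threaten the trial's main result.

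**What to change.** In SAP Efficacy Analyses 2 and 3, state that total-sample efficacy summaries are descriptive and that inference rests on the PTSD+ and CSO models already planned. This extends to all two-role scales what Protocol 12.0 already requires for relationship satisfaction.

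If a pooled test is kept, specify a mixed model with role, visit and role-by-visit, plus a dyad-level random effect or within-dyad covariance, and state the same structure for the MMRM fallback.

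Do not pool PCL-5, PTGI or TABS across roles, even descriptively. Report them as separate self-rated and partner-rated outcomes. While editing, settle what the CSO's TABS measures and who completes SORTS.

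The cost is a wording change and, if a pooled test is kept, a dyad-level RANDOM or REPEATED statement in the SAS code. No new data are needed. The price is fewer nominally significant pooled results.

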12.0 Data Analysis

Key Personnel, MAPS, and the biostatistician will agree on a Statistical Analysis Plan at the beginning of the study. The biostatistician will perform an Intent to Treat (ITT) analysis using repeated measures Analysis of Covariance (ANCOVA) to compare demographics and all available data from any participant receiving at least one Experimental Session and completing follow-up assessments from all participants, even if they withdraw from the allocated treatment prior to the Primary Endpoint.

This pilot study will test the impact of MDMA-assisted psychotherapy with CBCT for reducing PTSD and other psychological symptomology (e.g., depression) among a sample (N=10) of participants with PTSD. The primary measure will be a paired T-test of CAPS scores from Baseline to Primary Endpoint. In addition, to determine the strength of the treatment effect, pre to post (paired) mean differences effect size estimates will be calculated. Durability of effects will be examined by comparing changes from Baseline to the assessments at three and six months after the final Experimental Session using mixed-effects regression methods, which accounts for both missing data and the nesting of correlated longitudinal data within participants.

Effect sizes will be estimated for all outcome measures using Cohen's (1988) procedures (Cohen's d and small sample bias corrected Hedges' g) [194]. Effects on depression symptoms, psychological functioning, trauma-related beliefs, interpersonal closeness, and sleep quality will also be assessed for exploratory purposes. The biostatistician will conduct secondary analyses of self-report assessments using repeated measures ANCOVA. As a secondary outcome measure, weekly PCL-5 assessments will be conducted 15 times, starting at the second prep visit, weekly during treatment, and three follow-up assessments. To examine changes in PCL-5 over the 15 time points, the sponsor statistician will use linear mixed-effects regression with restricted maximum likelihood estimation, using weeks as a continuous variable. Measures of relationship satisfaction will be analyzed separately for participants with and without PTSD. Statistical significance will be determined based on $\alpha < .05$ for all tests other than the PCL-5, which will be a secondary measure for self-reported PTSD symptoms intended to support the CAPS.

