## 6.0 Analyses

In general, nominal variables will be described in terms of frequencies and percentages and analyzed using chi square analysis. Ordinal and non-normal continuous variables will be described using sample median and range, and analyzed by non-parametric statistical tests, and approximately normal variables will be described using sample mean and standard deviations and analyzed by parametric statistical tests. All statistical tests will be two-sided and a difference resulting in a p-value of less than or equal to 0.05 will be considered statistically significant. All p-values will be rounded to and displayed in four decimals. P-value less than 0.0001 will be shown in tables as <0.0001. For any analysis that is called out as parametric, e.g. t-test, the parametric assumptions will be examined. If necessary, nonparametric analyses will be utilized, e.g. Wilcoxon rank-sum test.

Clinical data will be presented in tabular format. Data not subject to analysis according to this plan will not appear in any tables or graphs but will be included in the data listings. Analyses will be carried out with SAS Version 9.4 (or higher). Selected results may be presented graphically using standard graphical software.

Post-hoc exploratory analyses not identified in this SAP may be performed to further examine the study data. These analyses will be clearly identified as such in the final clinical study report.

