# Handling of Dropouts, Missing Data

Dyads who discontinue treatment prior to completing the second experimental session and the primary endpoint will be replaced. These dropout subjects will be asked to complete an outcome assessment prior to continuing to the long-term follow-up.

Early termination visit data for mITT and Safety variables will be analyzed at the closest scheduled visit after the last experimental session completed. If the closest visit has valid data, the early termination data will be assigned to the next available visit. If a dyad discontinues and does not participate in an early termination visit, data from the last available visit will be used to replace the missing early termination visit data.

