#### **Protocol Deviations**

All protocol deviations will be included as a categorized listing. Safety and mITT analyses will include all enrolled dyads with all available data. Dyads with major deviations will be excluded from the per protocol analyses. Possible protocol deviations include the following seven categories:

- Subject entered study but did not meet criteria
- Subject developed withdrawal criteria but was not withdrawn
- Subject received excluded concomitant treatment
- Protocol procedure not performed per protocol
- Subject received incorrect treatment or incorrect dose
- Protocol procedure performed out of range
- Miscellaneous

The number of dyads in each protocol deviation category listed below will be summarized by MDMA group, and individual subjects will be listed in the appendix.

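### The SAP's three-visit repeated-measures ANOVA for the secondary self-report measures has no rule for a form missed by a participant who stays in the study

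*SAP*

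**What the plan says.** **The model.** SAP section 6.0, efficacy section 2 (Secondary and Exploratory Efficacy Analyses), lists 17 measures and says that "a one-way repeated-measures ANOVA with post-hoc contrast comparisons will be conducted to test the effects of the treatment on" them. The outcomes "will be assessed at baseline, midpoint (visit 9), and primary endpoint (visit 16) to examine change in scores over time in the total sample", and also separately for PTSD+ and CSO participants. The section says nothing about missing scores.

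**The missing-data rules elsewhere.**
- SAP efficacy section 3 (Long-Term Follow-up): "If data is missing from participant dropouts a mixed effect model repeat measures (MMRM) will be used instead of an ANCOVA".
- SAP, Handling of Dropouts, Missing Data: when a dyad discontinues and has no early termination visit, "data from the last available visit will be used to replace the missing early termination visit data".
- SAP, Protocol Deviations: "Safety and mITT analyses will include all enrolled dyads with all available data".

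**The protocol.** Section 12.0 also intends to use all available data. It plans repeated-measures ANCOVA for the self-report assessments and linear mixed-effects regression for PCL-5. For durability at three and six months it plans "mixed-effects regression methods, which accounts for both missing data and the nesting of correlated longitudinal data within participants".

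**The concern.** A participant who attends throughout but leaves one visit 9 questionnaire blank is neither a dropout nor a discontinued dyad, so no missing-data rule applies. What happens to that person's baseline and visit 16 scores then depends on how the ANOVA is programmed. The usual repeated-measures ANOVA needs a full row per participant, and with one score missing the whole row is lost.

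Each separate analysis has at most 10 people, and CSI may have fewer because it is for romantic couples only. Protocol section 5.2.7 sets a battery of 16 questionnaires at visit 9, including the 80-item IPF. Different people could drop out of different measures, so the tests for different outcomes would rest on different subsets. At stake are the tests and contrasts for the secondary outcomes in a study whose results, according to SAP section 2.0, will help to design a larger one.

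**Working it through.** **1. Which rule covers which case.**

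| Situation | Rule in the SAP |
|---|---|
| Dyad discontinues, no early termination visit | Last available visit carried forward |
| Data missing from dropouts, long-term analysis | MMRM replaces ANCOVA |
| Participant continues, visit 9 form missing, section 2 analysis | None |

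The SAP treats the MMRM as a different method, used in place of ANCOVA. The word ANOVA in section 2 therefore cannot safely be read as already meaning a mixed model.

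**2. Which measures are exposed.** Of the 17 listed, CAPS-5 is not collected at visit 9 (Time and Events tables in both documents; protocol Table 4). That leaves 16. A three-visit ANOVA of CAPS-5 has no complete row and cannot be run as written.

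**3. Reproducing the protocol's power.** Inputs: n = 10 and effect size 0.8 (protocol section 12.1); "All statistical tests will be two-sided" and "a p-value of less than or equal to 0.05 will be considered statistically significant" (SAP section 6.0). For a paired t-test, df = n − 1 and the noncentrality is 0.8 × √n. At n = 10, df = 9, the critical value is 2.262, the noncentrality is 0.8 × 3.162 = 2.530, and power is 61.6%. This agrees with the protocol's 62%.

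**4. Losing participants.** The same formula, applied to a secondary measure, with the 95% confidence half-width for mean change equal to t(0.975, n − 1)/√n in SDs of change:

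| Complete rows | Power | Half-width | ANOVA error df, 2(n − 1) |
|---|---|---|---|
| 10 | 61.6% | 0.715 | 18 |
| 9 | 55.9% | 0.769 | 16 |
| 8 | 49.6% | 0.836 | 14 |

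One lost row widens the interval by 0.769/0.715 − 1, about 7%.

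**5. Assumed rates of missed visit 9 forms.** The documents give no rate. With rate m, the chance of losing at least one of 10 people on a given measure is 1 − (1 − m)^10. Average power weights the power at each n by the Binomial(10, 1 − m) probability.

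| m | At least one lost | Average power |
|---|---|---|
| 2% | 18% | 60.5% |
| 5% | 40% | 58.7% |
| 10% | 65% | 55.7% |
| 20% | 89% | 49.2% |

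**6. A worked data set.** One set of 10 participants and three visits was simulated and one visit 9 score deleted. A standard repeated-measures ANOVA routine rejected the data as unbalanced. The nine complete rows gave a baseline-to-endpoint change of −0.647. A REML mixed model used 29 of the 30 scores and gave −0.664, the same as the mean over all 10 pairs.

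**The case against.** **Row deletion is not stated.** A reader might infer that the SAP prescribes complete-case analysis and that one missed form must remove that person's change score. Neither document says so. An ANOVA fitted with participant and visit as factors to the long-format data keeps the observed pairs: in the data set of step 6 it also gave −0.664. This objection stands. The defect is that section 2 does not say how it will use all available data, and that the standard form of the named method would not.

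**Effect sizes.** A reader might also infer that the reported effect sizes shrink to fewer people. They do not. Under the SAP's Efficacy Analyses heading, Hedges' g uses baseline and follow-up means and SDs, so visit 9 does not enter. The primary paired t-test does not use it either.

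**Scope.** Not every secondary outcome is exposed in the same way. CAPS-5 has no visit 9 score, and the protocol already gives PCL-5 a mixed model. The total-sample analysis has 20 people, not 10. The protocol's words on mixed-effects regression and missing data concern durability at three and six months, not visit 16.

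**Size.** The power figures are for a paired contrast, not the omnibus F test. With the pooled ANOVA error and sphericity, the levels are higher (66.8% at n = 10, 61.6% at n = 9), but the drop for one lost row is similar. The value 0.8 was set for the primary measure, and the protocol says no power estimates were available for the secondary ones. Visit 9 is an in-person visit, so missed forms there may be few.

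**Bias.** People who skip the battery may differ in outcome, but nothing in the documents shows that they would.

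**Importance.** These are exploratory outcomes in a pilot that is not meant to lead to registration. That limits the consequence, but the remedy is a short wording change.

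**Conclusion.** The point holds as a gap in specification. SAP efficacy section 2 names a method whose standard form discards observed baseline and visit 16 scores when a visit 9 form is missing, and no missing-data rule reaches a participant who stays in the study. This conflicts with the SAP's own statement on available data.

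The effect is confined to the section 2 tests and contrasts. One lost participant costs about 6 percentage points of power (61.6% to 55.9%) and two cost about 12 (to 49.6%). These figures assume complete-row deletion, a borrowed effect size of 0.8, and missed-form rates for which the documents offer no basis. Bias is possible but not shown.

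The change should be made: it is cheap, and it settles the method before anyone sees which forms are missing.

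**What to change.** In SAP efficacy section 2:

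- For the measures collected at visit 9, replace the repeated-measures ANOVA with the MMRM that section 3 already names, whatever the reason for missingness. Take baseline, visit 9 and visit 16 as repeated outcomes, visit as a fixed effect, unstructured covariance and Kenward-Roger degrees of freedom. Report the visit 16 minus baseline contrast.
- Fit it separately for PTSD+ and CSO participants. In any total-sample model, add a correlation between the two members of a dyad.
- Remove visit 9 from the CAPS-5 model.
- Align the PCL-5 model with the mixed-effects regression in protocol section 12.0.
- Name a simpler fallback covariance, because an unstructured fit may not converge with 10 participants.

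The cost is SAP wording and a different SAS procedure. No new data are needed.
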